## **II. Criteria for selecting study participants.**

### **1. Number of participants. (91 patients), will be divided into 3 groups**

1. The first group (n=31) included patients who received enteral nutrition (EN) after surgery.
2. The second group (n=30) included patients receiving parenteral nutrition (PN).
3. The third group (n=30) receiving mixed nutrition (MN), as is commonly considered the method of partial parenteral nutrition, in the early postoperative period.

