## **1. Methods and procedures.**

At the first stage, modern ideas about methods for assessing nutritional status and methods of nutritional support in the early postoperative period of patients operated on for malignant tumors of the hepatopancreatoduodenal zone were studied.

At the second stage, taking into account the need to select the optimal method of nutritional support in the early postoperative period, patients underwent an intragroup and intergroup comparative analysis of the main clinical and laboratory indicators, reflecting the most satisfactory dynamics of plastic processes regarding the type of nutritional support: enteral, parenteral and mixed.

To solve these problems, a prospective, longitudinal, parallel study and retrospective analysis of the results of treatment of 91 patients with malignant tumors of the hepatopancreatoduodenal zone who underwent the following operations were carried out:

- 1) resection of various segments of the liver;
- 2) hemihepatectomy;
- 3) transhepatic drainage of the right and left hepatic duct;
- 4) bypass gastroenteroanastomosis or cholecystoenteroanastomosis with interintestinal enteroenteroanastomosis according to Brown;
- 5) gastro-pancreatoduodenal resection;
- 6) corporecaudal resection of the pancreas with splenectomy.

The study was carried out on the basis of the KGP at the RVC "Multidisciplinary Hospital No. 3 of the city of Karaganda". Venue: intensive care unit.

To identify nutritional deficiencies, there are screening methods recommended by the international clinical nutrition associations ASPEN (American Society for Parenteral and Enteral Nutrition - ASPEN) and ESPEN (European Society for Parenteral and Enteral Nutrition - ESPEN), including questioning patients, using standard anthropometric and laboratory data, which makes it possible to assess nutritional status and the degree of its impairment.

At the first stage, the clinical condition of the patient was assessed using the Nutritional Risk Screening (NRS, 2002), Subjective Global Assessment (SGA) and Nutritional Risk Index (NRI) protocols before surgery and on the 5th, 10th, 15th day after surgery .

A comparative assessment of the clinical effectiveness of the use of types of nutritional nutrition in a complex of therapeutic measures after these operations in the hepatopancreatoduodenal zone was carried out.

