A comparative analysis of the dynamics of ALT and ASAT values in all patients in the study groups on the 2-3, 6-8, 10-12 days of the postoperative period reflected an excess of their normal values after surgery in some patients tens of times in the first day of the postoperative period. These changes can be explained, first of all, by the surgical intervention itself and its volume, the underlying disease of the hepatopancreatoduodenal zone and the associated cytolytic syndrome against the background of cholestasis [9,10,11].

In terms of assessing the dynamics of blood transaminase levels, in the majority of patients in the first group (78.2%), by the 5th and 10th days there was a decrease in ALT and AST values, on average, by 32.1 and 40.15%, respectively.

In the overwhelming number of patients in the second group (81.6%,  $n=26$ ), a statistically significant decrease in the level of these blood transaminases was also recorded, on average by 72.2% by the fifth day and 66.7% by the 10th day of the postoperative period from level of their initial indicator.

With a mixed type of nutritional support, by the 5th day of the postoperative period, the average significant decrease in transaminases was, on average, up to 72.6% of the initial values ( $p = 0.000$ ); by the 10th day of the postoperative period, their level decreased to 63.8% from the previous achieved value of 5 days ( $p=0.008$ ).

When comparing analyzes of the level of total blood bilirubin in patients of all nutrition groups, there was a strong direct correlation with a decrease in the level of blood transaminases, which, apparently, was also due to the creation of sufficient intraoperative bile outflow due to drainage of the biliary tract and elimination of the cause of obstructive jaundice (tumor).

However, high values of total blood bilirubin that persisted on the first day after surgery were due to temporary swelling of the biliary tract, which caused the excess of the norm by more than 10 times ( $p = 0.000$ ).

On days 5-7, there was a tendency towards a 5-6 fold decrease in its level from the initial values, which gradually decreased to normal values by days 10-12 and in some patients persisted until discharge from the hospital ( $p = 0.004$ ).

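### Six operations are pooled and the nutrition arms compared without adjustment, so arm differences in bilirubin, ALT and AST may partly reflect operation mix

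*Combined protocol and SAP*

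**What the plan says.** The protocol (III.1, Methods and procedures) describes "a prospective, longitudinal, parallel study and retrospective analysis of the results of treatment of 91 patients" who had one of six listed operations. The list covers liver segment resection, hemihepatectomy, "transhepatic drainage of the right and left hepatic duct", bypass anastomoses, "gastro-pancreatoduodenal resection" and distal pancreatic resection with splenectomy.

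Arms are defined by the feeding received (II.1, Number of participants): "The first group (n=31) included patients who received enteral nutrition (EN) after surgery", and likewise 30 parenteral and 30 mixed. Section V.1 mentions random selection of patients. It does not describe random allocation to an arm or stratification by operation.

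For analysis, the protocol (III.2, Data analysis and monitoring) plans Student's t-test and Pearson correlation. The report (Methods of statistical data analysis) uses an overall three-group test followed by pairwise t or Mann-Whitney tests. Neither includes an operation factor or the preoperative value as a covariate.

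In its results, the report explains the first-day transaminase excess first of all "by the surgical intervention itself and its volume, the underlying disease of the hepatopancreatoduodenal zone", together with cytolysis and cholestasis. It says the bilirubin fall was apparently "due to the creation of sufficient intraoperative bile outflow due to drainage of the biliary tract", and adds removal of the tumour that caused the jaundice. It then sets out transaminases and bilirubin arm by arm.

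**The concern.** Objective 2 asks how liver function evolves under each type of nutrition. The report's own account makes the operation a determinant of the markers used to answer that. If feeding route went along with operation type, or the mix differed by chance, the arms would differ in bilirubin, ALT and AST with no nutrition effect at all. Nothing described in the design prevents this, and nothing in the analysis would detect or correct it. The operation and the preoperative value are both on record for these patients, so leaving them out gives up a correction for bias and some precision at almost no saving.

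**Working it through.** The documents give no sample-size or power figure that bears on this point, so there is none to reproduce. Arm sizes are consistent: 31 + 30 + 30 = 91.

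**Observed gaps in the bilirubin fall** (report, results):

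| | Enteral | Parenteral | Mixed |
|---|---|---|---|
| Day 5 | not given | 40.09% | 20.0% |
| Day 10 | 12.7% | 45.0% | 44.0% |

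- Day 10, parenteral minus enteral: 45.0 − 12.7 = 32.3 points.
- Day 10, mixed minus enteral: 44.0 − 12.7 = 31.3 points.
- Day 10, parenteral minus mixed: 45.0 − 44.0 = 1.0 point.
- Day 5, parenteral minus mixed: 40.09 − 20.0 = 20.09 points.

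The preoperative reference is stated for the parenteral arm; I assume it for the other two.

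**What a difference in mix could produce.** Let D be the difference in mean percentage fall between operations that relieve biliary obstruction and those that do not. Let s be the difference between two arms in the share of relieving operations. Then the spurious gap is D × s. Neither quantity is in the documents, so I take D from 40 to 100 points as an assumption. The top of that range is extreme: a fall cannot exceed 100%, so D = 100 requires no average fall, or a rise, in the other class.

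- s = 20 points: 40 × 0.2 = 8 and 100 × 0.2 = 20 points, or 8/32.3 = 25% to 20/32.3 = 62% of the largest gap.
- s = 30 points: 40 × 0.3 = 12 and 100 × 0.3 = 30 points.

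To produce the whole 32.3 points, s must equal 32.3/D: 32.3 points at D = 100, 40.4 at D = 80 and 53.8 at D = 60.

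**How much imbalance chance alone gives.** I simulated simple random allocation of 91 patients to arms of 31, 30 and 30 (200,000 draws), assuming that 20% to 50% had a relieving operation.

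| Imbalance in share | Highest minus lowest of three arms | Enteral vs parenteral |
|---|---|---|
| 20 points or more | 14.5% to 29.7% of draws | 5.5% to 12.6% |
| 30 points or more | 1.1% to 6.0% | 0.3% to 2.1% |

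A 20-point spread somewhere among the arms is thus not unusual even under randomisation. An imbalance large enough to explain the whole enteral–parenteral gap would be rare under randomisation. Since random allocation is not described, these probabilities do not bound what happened here.

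**A measured baseline factor for comparison.** Preoperative SGA was normal in 24/31 = 77.4% (enteral), 19/30 = 63.3% (parenteral) and 17/30 = 56.7% (mixed), a spread of about 21 points. Chance could produce this, and it says nothing directly about operations, but it shows that imbalance of the illustrated size occurs in these arms.

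**The case against.** - **The report's attribution is narrower than it first looks.** The operation is offered for the first-day transaminase excess, alongside disease and cholestasis, not for the later falls compared by arm. The bilirubin explanation is hedged and credits tumour removal as well as drainage. This stands. It also means that a simple split into drained and undrained patients would misclassify some: a resection that removes the obstruction belongs with the relieving operations, and the bypass item covers both gastric and biliary anastomoses.
- **The day-5 gap is weak evidence.** The 20.09 points between parenteral and mixed shrink to 1.0 by day 10. A fixed difference in operation mix would have to explain both. This stands, so I do not rely on that gap.
- **Chance rarely explains the whole of the largest gap.** This stands. The case depends mainly on the undescribed allocation.
- **The reach is limited.** The bilirubin p-values (0.187 enteral, 0.002 parenteral) read as within-arm changes, and no between-arm p-value is given. The report's conclusions rest on NRI/SGA, total protein and basal metabolism. This stands, and it confines the direct harm to objective 2.
- **Pooling is a legitimate choice.** The stated purpose covers operations across the whole hepatopancreatoduodenal zone. Agreed: the fault is the missing adjustment, not the breadth.

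A reader might go further and infer that the bilirubin differences are a surgical artefact. The documents do not support that. Operation mix by arm is not in the available text, and a figure that follows the bilirubin results is not shown.

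**Conclusion.** The concern holds as possible, unaddressed confounding. Six operations are pooled, allocation to arm is not described as random, the comparisons are unadjusted, and the report names the operation as a cause of the markers compared. Differences between arms in bilirubin, ALT and AST cannot be attributed to nutrition on the present analysis.

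The size is unknown. Under the assumed 40 to 100 point contrast between operation classes, a 20-point imbalance accounts for 8 to 20 of the 32.3 points between enteral and parenteral at day 10. Accounting for all of it needs 32 to 54 points of imbalance even at contrasts of 60 to 100. These figures illustrate scale; they do not estimate bias.

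It would also be too strong to say that total protein, SGA or NRI must differ by operation. The documents give no operation-specific account of them, so adjustment there is a precaution. This is a change that should be made because it is nearly free, not because bias has been demonstrated.

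**What to change.** In the report's Methods of statistical data analysis:

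1. Tabulate operation class by arm, and state how patients came to be in each arm.
2. For between-arm comparisons of bilirubin, ALT, AST and total protein, replace the unadjusted tests with a linear model (ANCOVA, on a transformed scale if skewed) containing arm, preoperative value and a small operation-class factor.
3. Define the class from each patient's operation record, not from the list item. For bilirubin: biliary obstruction relieved by drainage, biliary bypass or resection, versus not. For ALT and AST: liver resection versus other. For total protein, name the class before the model is run.
4. For SGA and NRI, which are ordered categories, use an ordinal model or a rank analysis stratified by operation class.
5. Label this a post hoc reanalysis, since the study was completed in March 2020. If an arm difference in bilirubin, ALT or AST does not persist after adjustment, do not attribute it to nutrition.

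The cost is one or two degrees of freedom and one table, with no new data collection. The drawback is small cells. With 30 per arm, a two-class split gives about 30 × 0.5 = 15 per cell at a 50% share but only 30 × 0.2 = 6 at 20%. Six separate operations would average 30/6 = 5 per arm, which is why the factor should stay coarse.

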43-87% of patients with malignant neoplasms of various localizations have pronounced disturbances in body composition, which correlate with the prevalence of the tumor process and are aggravated during combined treatment. This is based on disturbances in protein, carbohydrate and fat metabolism caused by the systemic effect of the tumor on the body. Violation of nutritional status has a significant impact on the outcome and prognosis of the disease, inevitably increases the duration and cost of treatment, contributes to an increase in mortality and the number of complications, such as infection, slower wound repair, immunosuppression, hemocoagulation disorders, decreased concentrations of blood plasma proteins and a number of enzymes, metabolic disorders medications, decreased tolerance to surgical treatment, radiation and chemotherapy. BUT. Stadley showed that when depleted patients lost 20% of their initial body weight, mortality after surgery reached 33%, and in non-depleted patients -3.5%. According to B.R. Bistrian, G.L. Blakburn, with a 5% decrease in body weight during hospital stay, the length of stay increases by 2 times, and the frequency of complications increases by 3.3 times. J.L. Mullen and G.P. Buzby (1980) showed that impaired nutritional status in surgical patients leads to an increase in postoperative complications by 6 times, and mortality by 11 times, while timely administration of adequate nutritional therapy to such depleted patients reduces the number of postoperative complications by 2-fold. 3 times, and lethality - 7 times.

In this regard, the importance of accurately assessing the nutritional status of patients is obvious, which is the first step in treating and preventing further progression of malnutrition. A variety of methods are used to assess a patient's nutritional status. The use of enteral nutrition in the postoperative period contributes to the rapid elimination of intestinal paresis, early activation of intestinal motility, improved regeneration of the intestinal mucosa and activation of its absorption function.

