Some nutritional status indicators available for determination at the Oncology Clinic were assessed - body mass index (weight measurements were carried out before surgery, on the 5th, 10th and 15th days), basal metabolic rate (calculated using the Harris-Benedict equation, based on anthropometric data of the patient (gender, age, weight and height).), laboratory parameters: blood hemoglobin, lymphocytes, total protein, serum albumin, serum transferrin, total bilirubin and direct, ALT, AST, which are related to the traditional method for assessing nutritional status.

Additionally, we assessed the duration of postoperative gastostasis, the timing of the onset of intestinal motility, the appearance of stool, the return to a normal diet, the length of patients' stay in the ICU, the readmission of patients to the ICU and the duration of the postoperative bed-day, and the incidence of complications was calculated.

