As can be seen from the presented data, in the preoperative period, according to the SGA assessment, 24 patients in the enteral group, 19 patients in the parenteral group, and 17 patients in the mixed group had normal nutritional status before surgery, with variations relative to patients with moderate to severe malnutrition. Assessment of nutritional status before surgery using the NRI scale allowed us to confirm the nutritional status of the vast majority of patients in all groups as relatively normal

Thus, in 62 of the 91 patients examined, the NRI was assessed as true negative (normal nutritional status), in 26 as true positive (moderate malnutrition), and in 3 as severe malnutrition. Data from the NRI method during this time period had a strong correlation with the results of the SGA scale ( $p < 0.005$ ).

On the 10-12th day of the postoperative period in patients of the “enteral” group, the results of the assessment on the SGA scale remained unchanged; according to the NRI rating scale, there was an increase in “moderate malnutrition” per patient (25%).

With parenteral nutritional support, 17 patients had “normal nutrition”, 14 patients had moderate malnutrition, with regression of “severe malnutrition” in 1 patient. In the mixed nutrition group, there was a complete elimination of signs of “severe malnutrition” by 100% according to the given scales ( $p < 0.005$ ).

In patients of all study groups, throughout the entire period of nutritional support, fluctuations in the level of basal metabolism were observed in average values of  $335.89 \pm 53.6$  kcal/day (13.44%) from the initial value - 1-2 days of the postoperative period and were due to variability body mass index and the dynamics of the temperature curve after surgery.

In patients in the groups with enteral and parenteral nutrition, by the end of these types of energy subsidies (days 10-15), the level of basal metabolism was observed to approach its initial values -  $2500.1 \pm 353.4$  kcal/day and  $2350.0 \pm 330.5$  kcal/day days accordingly. With a mixed type of nutrition, there was a statistically significant decrease in the level of basal metabolism by 6.78% ( $2250.0 \pm 105.2$  kcal/s), which allows us to conclude that patients' energy costs are more effectively covered with this option of nutritional support in a comparative aspect with isolated types nutrition ( $p < 0.03$ ).

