### **Conclusion:**

1. According to the NRI nutritional status assessment scales, the SGA mixed type of nutritional support at the time of transfer of patients to the specialized department and upon completion of this area of intensive therapy in the specialized department by 12-15 days of the postoperative period showed higher effectiveness in stabilizing the condition and maintaining the patients' caloric intake in a comparative aspect with the group of isolated enteral nutrition and parenteral nutrition.
2. Throughout the entire period of isolated enteral, parenteral and mixed nutritional support, all patients (100%) showed a relatively constant level of total blood protein.
3. In patients of all three groups, throughout the entire period of nutritional support, fluctuations in the level of basal metabolism were observed, which was due to the variability of body mass index and the dynamics of the temperature curve after surgery. In patients in the groups with enteral and parenteral nutrition, by the end of nutritional support (days 15-20), the level of basal metabolism was observed to approach its initial values. With a mixed type of nutrition, a statistically significant decrease in the level of basal metabolic rate was observed, which suggests a more effective coverage of the energy costs of patients with this option of replenishing nutritional ingredients.

**Researcher:** [name], PhD student KSMU

[contact].

e-mail: [contact].

[figure not shown]
Signature  17.03.2020

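### Weight and BMI are said to be measured four times and are used to explain the basal metabolism changes, but no value is reported for any arm, so the 6.78% fall with mixed feeding cannot by itself count as better feeding

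*Combined protocol and SAP*

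**What the plan says.** Section III.1 of the protocol lists the nutritional status indicators and puts first "body mass index (weight measurements were carried out before surgery, on the 5th, 10th and 15th days". The report's Clinical research program repeats the schedule. Both describe basal metabolic rate as "calculated using the Harris-Benedict equation, based on anthropometric data of the patient (gender, age, weight and height"; no other input is listed.

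The Introduction explains why weight matters, citing earlier work in which "with a 5% decrease in body weight during hospital stay, the length of stay increases by 2 times" and complications become 3.3 times as frequent. Objective 1 is to compare the course of nutritional deficiency and nutritional status across the three types of support.

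The report's Results and discussion says that basal metabolism fluctuations in all groups "were due to variability body mass index and the dynamics of the temperature curve after surgery". Conclusion 3 repeats the explanation: "which was due to the variability of body mass index and the dynamics of the temperature curve after surgery". For the mixed arm the report states that "there was a statistically significant decrease in the level of basal metabolism by 6.78" per cent, and concludes that "patients' energy costs are more effectively covered with this option of nutritional support". Conclusion 3 carries the same reading. Conclusion 1 separately calls mixed support more effective on the NRI and SGA scales.

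**The concern.** BMI is planned, stated as measured and then used as an explanation, but its values are not shown. Basal metabolism, which is calculated partly from weight, is shown and is used to rank the arms.

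The two readings of basal metabolism also sit badly together. Its changes across all groups are put down to BMI and temperature, while its fall in the mixed arm is put down to better feeding. If the figures come from the stated calculation, a fall within a patient points to lost weight, which the study's own background calls harmful. The same number could then accompany benefit or harm, and the reader lacks the data to tell which. Conclusion 3 depends directly on the answer, and the answer to objective 1 is incomplete without it.

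**Working it through.** **1. Is any weight or BMI result reported?** Three arms at four weighings (before surgery, days 5, 10 and 15) give 3 × 4 = 12 cells. The readable results cover SGA and NRI categories, basal metabolism, total protein, lymphocytes, transaminases and bilirubin. Weight or BMI cells filled: 0 of 12. One figure after the bilirubin text and one at the signature are not visible. No text refers to a weight or BMI figure, but their content cannot be checked.

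**2. The reported basal metabolism figures.** Means at the end of support are 2500.1 (enteral), 2350.0 (parenteral) and 2250.0 (mixed) kcal/day. The mixed arm's starting value is not stated, so the 6.78% cannot be reproduced directly. Working back:
- Mixed arm: 2250.0 / (1 − 0.0678) = 2413.6 kcal/day at the start, a fall of 163.6.
- All groups: the fluctuation of 335.89 kcal/day is given as 13.44% of the initial value, so that value is 335.89 / 0.1344 = 2499 kcal/day.

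**3. What can move the stated calculation?** Within a patient over two weeks, gender and height are fixed and age is nearly so. Write calculated basal metabolism as B = c + kW, where W is weight and c holds the other inputs. Then

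% change in B = s × % change in W, with s = kW / B.

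Weight is the only listed input that can produce a material fall. When c is positive, s is below 1, and the percentage loss of weight must exceed the percentage fall in B. With s assumed between 0.4 and 0.7 (not in the documents), a 5% weight loss lowers B by only 5 × 0.4 = 2.0% to 5 × 0.7 = 3.5%.

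**4. Does the stated calculation produce figures of the reported size?** Assume the usual published Harris-Benedict coefficients, which the documents do not give, with weights of 60–85 kg, heights of 160–175 cm and ages of 50–70 years.

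| | Calculated, kcal/day | Reported arm means, kcal/day |
|---|---|---|
| Men | 1219–1773 | 2250–2500 |
| Women | 1198–1558 | 2250–2500 |

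The lowest reported mean is 2250 / 1773 = 1.27 times the highest calculated value. On the same coefficients, a 50-year-old man of 175 cm would have to weigh about 132 kg to reach 2414 kcal/day. Either the body sizes were unusual or something beyond the listed inputs was applied.

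**5. What follows.** A constant multiplier cancels out of a percentage change, so the argument in step 3 would survive it. A multiplier that changes over time, for example with temperature, would not cancel, and part or all of the fall could then reflect temperature. In neither case does the fall show better feeding. Coverage of energy costs also depends on intake, and the readable results give no intake figures.

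**The case against.** The strongest objection is that weight loss is not the only candidate. The report names temperature alongside BMI, and the absolute values do not fit the listed inputs. This stands, and it limits the point to what the stated method implies.

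A reader might go further and convert the 6.78% into a weight loss. With the coefficients and body sizes above, that gives 9.1–11.7% in men and 12.0–15.6% in women, well past the 5% mark. The documents do not support this. The same assumptions fail to reproduce the reported kcal values, and losses of that size are implausible in two weeks. The baselines may also differ: the initial value appears to be taken on postoperative days 1–2 (the wording is unclear), when no weighing is scheduled.

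Other objections stand in part:
- Conclusion 1 rests on NRI and SGA. The report says that such screening uses anthropometric data, so weight may enter indirectly. That does not display weight change, but it means Conclusion 1 does not fall with Conclusion 3.
- Early postoperative weight is affected by fluid and drainage losses and by resected tissue. It needs careful reading and should not override the scales automatically.
- Albumin, transferrin, haemoglobin, ICU stay and complications also have no readable results, and the protocol sends findings to a dissertation and publications. The gap is not unique to weight. Weight differs because the report relies on BMI as an explanation and on a quantity computed from weight for a superiority claim.
- Day-15 weights are described as taken, but the repeated-measures tests name only baseline, day 5 and day 10. Completeness at day 15 is unknown.

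**Conclusion.** The point holds in a limited form. Weight and BMI are stated as measured at four times and invoked as a cause, yet none of the 12 arm-by-time values appears in the readable report. Under the calculation as described, the 6.78% fall in the mixed arm can come materially only from weight loss, so it cannot by itself support the claim of better energy coverage in Results and discussion and Conclusion 3.

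The direction of this inference rests on the listed inputs being the only ones used. Its size cannot be given, because the reported values exceed what the usual equation yields for typical body sizes and an unlisted factor may have been used. A reader might infer that mixed feeding caused harmful weight loss, or that Conclusion 1 must be withdrawn. The documents establish neither. The weights are needed to judge the first, and Conclusion 1 has a separate basis in NRI and SGA.

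**What to change.** 1. For each arm, report percentage weight change (numerically the same as percentage BMI change, since height is fixed) from the preoperative weighing to days 5 and 10, and to day 15 where recorded. Give n at each time, arm differences with 95% CIs adjusted for preoperative weight, and the number losing 5% or more.
2. State how basal metabolism was actually calculated: the coefficients, any temperature or other factor, which weight was used at each time, and which time is the initial value.
3. In Results and discussion and Conclusion 3, do not present the fall in basal metabolism as evidence of better feeding unless the weights show that it is not weight loss.
4. Read Conclusion 1 alongside the weight table, with no automatic rule for withdrawing it.

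The cost is one table and one adjusted comparison, from weighings that the report says were made. Precision should be useful. With 30 per arm and an assumed SD of weight change of 3 to 6 percentage points, the unadjusted 95% CI half-width for an arm difference is 1.96 × SD × √(2/30), or about 1.5 to 3.0 points. The drawbacks are that fluid shifts and resection complicate early weights, day 15 may be incomplete, and the claim for mixed feeding may weaken.
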